### 8.2. Analysis of the Efficacy Endpoints

#### 8.2.1. Primary Efficacy Analysis

Target Population: Adult patients with IgAN who are on a stable dose of SGLT2 inhibitor. The primary efficacy analysis will be based on the FAS.

Variable: Change from baseline to Week 24 in UA/C

Treatment Conditions: Sparsentan + SGLT2 inhibitor QD for 24 weeks

Intercurrent events: The following intercurrent events could impact the UA/C values of patients:

- Non-compliance with study drug
- Receipt of immunosuppressive steroids for renal indications
- Death or renal transplant

For all intercurrent events, an on-treatment policy will be used. Sensitivity analyses may be performed using the treatment policy (all on-study data used).

Population-level summary: The change from baseline (Day 1) UA/C at Week 24 will be analyzed via a MMRM analysis. The MMRM analysis will be performed using observed data with no imputation of missing data. The dependent variable will be UA/C change from baseline. As UA/C is a highly right-skewed variable, analyses will be performed on log-transformed data. The model will include the following fixed effects:

- Baseline UA/C in log scale
- Time (ie, analysis visit in weeks)

In addition, patient will be included as a random effect. An unstructured covariance matrix will be used. If the computational algorithm fails to converge, the following structures will be executed: heterogeneous Toeplitz, heterogeneous compound symmetry (CS), heterogeneous first-order autoregressive (AR[1]), Toeplitz, CS, and AR(1).

The least squares (LS) means, and 95% CI will be extracted from the model. Results will be back-transformed to present treatment effects on the ratio scale. Estimates and CIs will be converted to percentages via the following transformations:

$$(\exp [\text{LS mean change from baseline in natural log } \{\text{UA/C}\}] - 1) \times 100$$

Baseline value, absolute change from baseline to Week 24, and percent change from baseline to Week 24 will be summarized descriptively. Observed value, absolute change from baseline, and percent change from baseline at each visit will be summarized similarly and estimates from the MMRM at each visit will also be presented as described above for Week 24.

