6.6. Dose Modification

The Investigator may titrate up the participant's dose to the target dose based on BP and lack of AEs at Week 2. Participants who tolerate the initial dose after 2 weeks but display asymptomatic systolic BP values \leq 100 mmHg, or diastolic BP values \leq 60 mmHg will continue the initial dose after the Week 2 visit without titrating up to the target dose. Participants who do not titrate up to the target dose at Week 2 for any reason, may titrate up to target dose at any time thereafter based on evaluation of the Investigator and if allowed by BP and lack of AEs in consultation with the Medical Monitor as needed. Participants who do not tolerate the initial dose for any reason at the Week 2 visit may discontinue study intervention.

Throughout the study, participants will be maintained on the maximum allowed dose of study intervention they can tolerate while secondarily maintaining BP as close as possible to the target of 125/75 mmHg. To maintain BP, the Investigator will be encouraged to either treat participants with additional anti-hypertensive agents [with the exception of ACEIs, aliskiren, ARBs, or ERAs (see [Section 10.6](#))] or withdraw anti-hypertensive agents. In the case of intolerable hypotension, withdrawal of additional anti-hypertensive agents should be accomplished before considering withdrawal or dose reduction of study intervention.

Doses may be modified (titrate up or down) at any time throughout the study for safety or tolerability reasons at the Investigator's discretion, and if appropriate, additional safety testing may be performed.

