## **4.3. Sample Size Considerations**

### **4.3.1. Sample Size Justifications**

Approximately 60 participants will be enrolled in the study. The sample size of the study is determined empirically without formal statistical assumptions. A sample size of 60 is sufficient to detect at least 1 AE with probability 95%, assuming an expected AE incidence of 5% using the binomial distribution.

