## **4.4. Randomization**

This is a single-arm study; therefore, randomization is not applicable in this study.

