### 8.2.2.2. Absolute Change and Percent Change in eGFR and BP

Baseline value, absolute change from baseline at each visit, and percent change from baseline at each visit in eGFR and BP (Systolic and Diastolic) will be summarized descriptively. Additionally, change from Baseline to Week 24 will be analyzed via a MMRM model using observed data only. The dependent variable will be change from baseline. The model will include the following fixed effects:

- Baseline value
- Time (ie, analysis visit in weeks)

In addition, patient will be included as a random effect. The covariance matrix will be chosen similarly to as what is described in [Section 8.2.1](#). The LS means and 95% CI will be extracted from the model and presented for each visit.

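### The single-arm MMRM confidence intervals for mean change leave out the sampling variation of the baseline mean, so they are somewhat too narrow for the SAP's stated target population

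*SAP*

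**What the plan says.** The study has no comparator: "This is a single-arm study; therefore, randomization is not applicable in this study" (SAP 4.4). For the primary endpoint (SAP 8.2.1), "The dependent variable will be UA/C change from baseline", analysed on the log scale. The fixed effects are "Baseline UA/C in log scale" and visit. From this model, "The least squares (LS) means, and 95% CI will be extracted from the model", and the results are back-transformed to a percent change. The same section describes the adult IgAN population on a stable SGLT2 inhibitor as the target and labels the MMRM result a population-level summary.

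SAP 8.2.2.2 applies the same form to eGFR and to systolic and diastolic BP: "The LS means and 95% CI will be extracted from the model and presented for each visit". SAP 8.2.2.3 applies the UA/C analysis to UP/C. None of the three sections says at which baseline value the LS mean is read, or adjusts its variance because baseline is a sampled quantity.

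SAP 8.1 separately plans a descriptive mean change with a 95% CI where appropriate. Protocol 9.1 states that there is no efficacy hypothesis.

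**The concern.** In a randomised trial, adjusting for baseline sharpens the difference between arms, and sampling variation in the overall baseline mean largely cancels from that difference. With one arm nothing cancels. The reported quantity is the mean change, and part of its sampling variation comes from which baselines happened to be enrolled. A model that regresses change on baseline removes that part from the residual variance. Reading the LS mean at the sample's own mean baseline does not put it back. Degrees-of-freedom corrections do not restore it either.

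With no hypothesis test, the interval is the trial's main statement of uncertainty about the size of the effect. For UA/C, the MMRM interval is the named primary result and the only ratio-scale interval that SAP 8.2.1 spells out. If it is too short, the result looks more precise than it is. It may also sit beside a wider descriptive interval for a similar quantity, with no rule for which one counts.

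**Working it through.** **Inputs from the documents.** 95% intervals (SAP 8.2.1, 8.2.2.2); one arm (SAP 4.4); "Approximately 60 participants will be enrolled in the study" (SAP 4.3.1); model terms as above.

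**Inputs that are assumed.** The documents give no SDs or correlations. Let ρ be the correlation between the baseline and Week 24 values, and k the ratio of the Week 24 SD to the baseline SD. UA/C and UP/C are on the log scale.

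**The plan's own figure.** SAP 4.3.1 gives a 95% probability of seeing at least one AE at 5% incidence with n = 60. This reproduces: 1 - 0.95^60 = 0.954. It concerns AEs only; no precision is stated for any efficacy interval.

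**Derivation (complete data, Week 24).**
1. The LS mean at the observed mean baseline equals the sample mean change.
2. Its model-based variance is s²(residual)/n.
3. The variance of the mean change over repeated samples from the population is [s²(residual) + b²·s²(baseline)]/n, where b is the slope of change on baseline.
4. SE ratio = sqrt[s²(residual)/s²(change)] = sqrt(1 - r²). In terms of ρ and k this is k·sqrt(1 - ρ²) / sqrt(1 + k² - 2ρk). With k = 1 it reduces to sqrt[(1 + ρ)/2]. It never exceeds 1, and equals 1 only when ρk = 1, that is, when change is unrelated to baseline.
5. Actual coverage = P(|t58| < t_crit × ratio), for n = 60.

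**Equal SDs (k = 1), n = 60.** Example: ρ = 0.6 gives sqrt(1.6/2) = 0.894.

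| ρ | SE ratio | Interval too short by | Coverage, formula | Coverage, simulated |
|---|---|---|---|---|
| 0.5 | 0.866 | 13.4% | 91.2% | 91.2% |
| 0.6 | 0.894 | 10.6% | 92.1% | 92.3% |
| 0.7 | 0.922 | 7.8% | 93.0% | 93.1% |
| 0.8 | 0.949 | 5.1% | 93.7% | 94.1% |
| 0.9 | 0.975 | 2.5% | 94.4% | 94.5% |
| 0.95 | 0.987 | 1.3% | 94.7% | 94.6% |

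The simulation used the baseline-adjusted model on complete Week 24 data, 40,000 runs per row. In the same runs the plain interval for the mean change covered 95.0% to 95.3%. The adjusted interval, judged against the mean change expected for the enrolled baselines, covered 95.0% to 95.2%. A small repeated-measures simulation (unstructured covariance, 10% missing at Week 24, 400 runs, Monte Carlo error about 1.3 points) pointed the same way: 90.3%, 93.0%, 92.0%, 93.5% and 92.8% at ρ = 0.4, 0.5, 0.6, 0.7 and 0.8.

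**Unequal SDs.**
- UA/C or UP/C, wider spread at Week 24 (k = 1.2): 6.7% too short at ρ = 0.5, 1.7% at 0.7, 0.2% at 0.8.
- Narrower spread at Week 24 (k = 0.8): 20% to 29% too short for ρ from 0.3 to 0.95.
- Systolic BP, SD falling from 15 to 13 (k = 0.867): 25.5% at ρ = 0.3, 17.8% at 0.6.
- Systolic BP, SD rising from 13 to 15 (k = 1.154): 14.0% at ρ = 0.3, 5.1% at 0.6.

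**The case against.** **Coverage depends on the target.** Conditioning on observed covariates is ordinary regression practice, and on that reading the interval covers 95%. This stands as a statement about the enrolled baselines. But SAP 8.2.1 names a patient population and calls the result a population-level summary, and for that target the baseline term belongs in the variance.

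**An unaffected interval is already planned.** The descriptive interval in SAP 8.1 does not have this problem, and SAP 8.2.2.2 adds the MMRM to the descriptive summaries of eGFR and BP. A reader might infer that every efficacy interval is wrong; the documents do not support that, since only the MMRM intervals are affected. The descriptive interval does not dispose of the point, however, because the MMRM is the named primary analysis for UA/C.

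**Nothing is decided on the width.** There is no test, success threshold or comparator. This stands, and it limits the consequence.

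**The reference value is not SAP wording.** A reader might infer that the SAP prescribes reading at the observed mean baseline. It does not; that is the usual default, and the SAP is silent.

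**BP as the worst case.** Protocol 6.6 speaks of "maintaining BP as close as possible to the target of 125/75 mmHg", from which a reader might infer that change in BP must depend strongly on baseline. The same sentence ranks BP second, after keeping participants on the highest allowed dose they tolerate, and investigators are only encouraged to adjust other agents. BP may be affected more, but the documents cannot confirm it.

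**Conclusion.** The point holds for the MMRM intervals, provided that the LS mean is read at the observed mean baseline and the target is the population mean change. The direction is a mathematical result: the standard error is never too large on this account. The size rests wholly on assumed SDs and correlations:

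- Equal SDs, ρ 0.5 to 0.8: about 13% to 5% too short, coverage about 91% to 94%.
- UA/C: near zero if the Week 24 spread exceeds the baseline spread at ρ around 0.7 to 0.8.
- eGFR: about 1% to 3% if ρ is 0.9 or more with equal SDs, which is negligible.
- BP: about 5% to 25%, for SDs of 13 and 15 in either order and ρ 0.3 to 0.6.

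A reader might also infer a biased effect estimate; this mechanism does not bias it. The change is worth making because the interval is the headline statement of precision and the correction is cheap. It does not put the study's exploratory conclusions in doubt.

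**What to change.** In SAP 8.2.1, 8.2.2.2 and 8.2.2.3, do one of the following:

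1. Model baseline as a response: log UA/C, log UP/C, eGFR or BP at baseline and at all on-treatment visits, with visit as the fixed effect and an unstructured covariance. Report the Week 24 minus baseline contrast with its 95% CI, back-transformed for UA/C and UP/C. With complete data the point estimate is unchanged. Participants with only a baseline value are kept.
2. Keep the present model, state that LS means are read at the observed mean baseline, and take the CI from a bootstrap that resamples participants and recomputes that mean each time.

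Also state which interval is the reported one where the descriptive mean-change CI of SAP 8.1 differs from the model's.

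The cost is SAP wording, a few lines of code and slightly wider intervals. With equal SDs the widening is a factor of 1.155 at ρ = 0.5, 1.085 at 0.7 and 1.026 at 0.9. No change to data collection or sample size is needed.

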## 8.2.2. Secondary Efficacy Analysis

### 8.2.2.1. Responder Endpoints

The following responder endpoints will be summarized:

- Achievement of UA/C <0.2 g/g at Week 24
- Achievement of 30% reduction from Baseline in UA/C at Week 24
- Achievement of 50% reduction from Baseline in UA/C at Week 24

For each endpoint, the number and percentage of patients responding at Week 24 will be presented. The denominator will be the number of patients with a nonmissing result for the parameter at Week 24. The 95% CI for the percentage of subjects with will be generated from an exact binomial distribution. The analysis will be repeated for each visit for each endpoint.

### 8.2.2.2. Absolute Change and Percent Change in eGFR and BP

Baseline value, absolute change from baseline at each visit, and percent change from baseline at each visit in eGFR and BP (Systolic and Diastolic) will be summarized descriptively. Additionally, change from Baseline to Week 24 will be analyzed via a MMRM model using observed data only. The dependent variable will be change from baseline. The model will include the following fixed effects:

- Baseline value
- Time (ie, analysis visit in weeks)

In addition, patient will be included as a random effect. The covariance matrix will be chosen similarly to as what is described in [Section 8.2.1](#). The LS means and 95% CI will be extracted from the model and presented for each visit.

### **8.2.2.3. Absolute Change and Percent Change in UP/C**

UP/C will be summarized and analyzed similarly to UA/C as described in [Section 8.2.1](#).

## **8.2.3. Exploratory Efficacy Endpoints**

### **8.2.3.1. Continuous Endpoints**

Quantitative urinalysis parameters (protein excretion, albumin excretion, urea, and creatinine) will be summarized and analyzed similarly to UA/C as described in Section 8.2.1).

### **8.2.3.2. Responder Endpoints**

Achievement of UP/C  $<0.3$  g/g will be summarized similarly to the responder endpoints in [Section 8.2.2.1](#).

## **8.2.4. Sensitivity Analyses of Efficacy Endpoints**

Sensitivity analysis will be conducted based on the PPAS for the primary and secondary efficacy analyses.

Additionally, all analyses based on laboratory data (UA/C, UP/C, eGFR) described above may also be repeated with the inclusion of local laboratory data with the central data, if there is sufficient local laboratory data to warrant such analysis. For these analyses, the value observed closest to the target day will be chosen regardless of if it comes from the local or central laboratory.

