### **6.4.2. Quantitative Urinalysis Parameters**

Baseline for quantitative urinalysis parameters, including UA/C and UP/C, will be calculated as the average of the 2 FMV samples collected within 3 days prior to the Day 1 visit. If one of the samples is missing, the single sample will be used.

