### 6.6.1. Primary Analysis

UA/C and other quantitative urinalysis measures such as UP/C will be determined using FMV samples and will be calculated as the average of 2 FMV samples collected within 3 days prior to each visit. If 1 of the samples is missing, UA/C and UP/C from the single sample will be used.

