## **6.6.2. Local Laboratories**

The primary analyses will use central laboratory data only. As a sensitivity analysis, local laboratory data may be included with central laboratory data.

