## 8. EFFICACY

### 8.1. General Considerations

All efficacy analyses will be done descriptively on the FAS using observed data only. Change from baseline (or percent change from baseline, as appropriate) will be summarized with mean and 95% CI, as appropriate. For categorical efficacy endpoints, the proportion of participants in the category will be presented along with corresponding 95% CI.

The primary and secondary efficacy endpoint analyses based on the PPAS will be performed as sensitivity analyses. All primary efficacy analyses based on laboratory data will use central laboratory data only.

Albuminuria (UA/C) and proteinuria (UP/C) will be determined based on a FMV samples. As UA/C and UP/C are highly right-skewed variables, analyses will be performed on log-transformed data. For ease of interpretation, results will be presented in the original units.

The eGFR for each baseline and post-baseline visit will be determined using the Chronic Kidney Disease Epidemiology Collaboration ([Levey 2009](#)) formula for adults based on serum creatinine values from the visit.

For the purposes of efficacy analyses, an assessment is considered “on treatment” if it occurs after the first dose of study medication and no more than 3 days after last dose of study medication for the patient. Additionally, efficacy analyses may be repeated using all on-study data.

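### In the optional local-laboratory sensitivity analysis, the closest-to-target rule lets a single local urine value replace an available central two-sample average

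*SAP*

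**What the plan says.** The main analyses and the sensitivity analysis are separated in SAP 6.6.2: "The primary analyses will use central laboratory data only. As a sensitivity analysis, local laboratory data may be included with central laboratory data". SAP 8.1 repeats the central-only restriction for the primary efficacy analyses.

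SAP 8.2.4 describes the sensitivity analysis. It is optional and wide in scope: "all analyses based on laboratory data (UA/C, UP/C, eGFR) described above may also be repeated with the inclusion of local laboratory data". It is also conditional: "if there is sufficient local laboratory data to warrant such analysis". The selection rule is that "the value observed closest to the target day will be chosen regardless of if it comes from the local or central laboratory".

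The urine measures are not single readings. Under SAP 6.6.1 the visit value "will be calculated as the average of 2 FMV samples collected within 3 days prior to each visit", with a fallback: "If 1 of the samples is missing, UA/C and UP/C from the single sample will be used". Under SAP 6.4.2 the baseline "will be calculated as the average of the 2 FMV samples collected within 3 days prior to the Day 1 visit", with the same fallback. SAP 8.1 adds, without naming a laboratory: "Albuminuria (UA/C) and proteinuria (UP/C) will be determined based on a FMV samples".

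SAP 6.5.3 already uses closeness to the target day to choose among several assessments in a window, and takes the latest if two are equally distant. SAP Table 1 sets the Week 24 target at day 169, with a window of days 128 to 183 for quantitative urinalysis.

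**The concern.** Section 8.2.4 is a rule about precedence, and it gives the central average none. If a participant has both a central two-sample average and one local value in the same window, the choice depends only on distance from the target day. The more precise measurement, made by the same laboratory and method as the baseline, can be dropped.

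What is at stake is how the sensitivity analysis is read. If local values only filled empty windows, a difference from the primary result would show what the added local data do. Under the rule as written, the same difference could also come from replacing valid central data, and the two cannot be told apart. The repeated analyses include the responder endpoints of SAP 8.2.2.1 (UA/C below 0.2 g/g, and 30% and 50% reductions). There each participant's status rests on one Week 24 value, so noise or an assay offset in that value can change the classification.

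**Working it through.** The plan gives no figure on this point: no within-person SD for UA/C and no expected share of local values. Its only sample-size figure, a 95% chance of at least one adverse event with 60 participants at 5% incidence, reproduces (1 − 0.95^60 = 0.954) but does not enter here. The SDs, correlations and participant counts below are assumptions.

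**1. Can replacement happen?** Let the visit fall *v* days from target, with a local sample on the visit day and the central value dated *k* days earlier (*k* = 1, 2 or 3, assumed from the three-day collection period). The local value is strictly closer when |v| < |v − k|, that is, when v < k/2. The Protocol's Week 24 visit window is ±7 days, which gives 15 offsets:

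| k | Offsets where local is strictly closer | Ties |
|---|---|---|
| 1 | 8 of 15 | 0 |
| 2 | 8 of 15 | 1 |
| 3 | 9 of 15 | 0 |

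On these assumptions, replacement is an ordinary outcome whenever a visit-day local sample exists.

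**2. Precision of one replaced value.** Let s be the single-sample SD on the log scale and ρ the error correlation between two samples. The SD of the two-sample mean is s√((1 + ρ)/2), so the ratio of single to mean is √(2/(1 + ρ)):

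| ρ | Variance ratio | SD increase |
|---|---|---|
| 0 | 2.00 | 41% |
| 0.3 | 1.54 | 24% |
| 0.5 | 1.33 | 15% |

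**3. Measurement noise in the change from baseline, independent errors.**
- Central at both times: s²/2 + s²/2 = s².
- Central two-sample baseline, one local sample at follow-up: s²/2 + s² = 1.5s².
- SD ratio: √1.5 = 1.22, so about 22% higher.

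**4. Effect on the Week 24 mean.** Let b be the between-person SD of true log change and f the share of participants whose average is replaced. With equal local and central precision and nobody added, the SE ratio is √[(b² + s² + 0.5·f·s²)/(b² + s²)].
- b = 0.5, s = 0.35, f = 0.5: √(0.4031/0.3725) = 1.040, so 4.0%.
- Over b = 0.3 to 0.7 and s = 0.2 to 0.5: 0.2% to 1.8% at f = 10%, and 0.9% to 8.8% at f = 50%.

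**5. Offset from added participants.** Take b = 0.5, s = 0.35, 50 participants with central values and f = 30%, so 15 are replaced. Suppose *m* more have a local value only. The variance per person is 0.3725 for central and 0.4338 for replaced or local-only.
- m = 0: SE ratio 1.024.
- m = 2: 1.007.
- m = 5: √[((35 × 0.3725 + 20 × 0.4338)/55²)/(0.3725/50)] = 0.982.
- m = 10: 0.944.

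The direction of the net effect depends on f and m, which the documents do not give.

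**The case against.** The strongest reply is that little depends on this. The analysis may never be run, the primary analysis uses central data only, and the study tests no efficacy hypothesis. Protocol Appendix 3 assigns quantitative urinalysis to the central laboratory, so a local UA/C would be an extra test. Protocol 8.4.4 makes recording compulsory only for local results that change management or are judged clinically significant. Closeness to target is also the SAP's general selection rule. All of this stands, and it limits the importance of the point. It does not remove it, because if the analysis is run the rule still discards central averages.

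Several stronger inferences are tempting, and the documents do not support them.
- *The sensitivity analysis is noisier than the primary one.* Steps 4 and 5 show that the net effect can go either way.
- *Local urine need not be first-morning void.* SAP 8.1 states the FMV basis without limiting it by laboratory, and 8.2.4 does not waive it. What is missing is an explicit statement that it covers local values.
- *A local value always wins.* That needs a visit-day local sample, a visit on or before target, and a central average dated before the visit. The SAP does not say what date the average carries. If it carried the visit date, a visit-day local value would tie.
- *Single-sample values are peculiar to this analysis.* The fallback in 6.6.1 already admits them when one of the pair is missing. It gives no reason to discard a complete pair.

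**Conclusion.** The point holds as a minor one. As written, 8.2.4 lets one local value replace an available central two-sample average for UA/C or UP/C. Each replaced value has a measurement SD up to 41% higher (independent errors; about 24% at correlation 0.3 and 15% at 0.5), and the measurement noise in its change from a two-sample baseline is up to about 22% higher. These figures assume that one local sample is as precise as one central sample. The replaced value is also not like-for-like with the central baseline.

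The effect on the Week 24 mean is modest under the assumed SDs, and its sign is not settled. A reader might infer that the sensitivity analysis would be uninterpretable, but that goes too far. Its comparison with the primary result would be harder to read because two changes are made at once. The loss of a two-sample average concerns urine only, since eGFR has none to lose. No primary result is affected.

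**What to change.** Replace the selection sentence in SAP 8.2.4 with wording such as:

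> A local laboratory value is used only when no central laboratory value exists in the analysis window. A central value is never replaced by a local value. The FMV basis in Section 8.1 applies to local UA/C and UP/C values. The number of local values used will be reported by visit.

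With central precedence, the date assigned to the two-sample average no longer decides between laboratories.

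The cost is a few lines of SAP text and one count per visit, with no new data collection. The downside is small: some selected values will lie slightly further from the target day. The change does not remove the mixing of a central baseline with a local follow-up value where a gap is filled. That comes with any use of local data, and the reported counts let the reader judge its extent.
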